4.4 Follow up

All patients will be followed up until day 90 after enrolment. Data will be collected by accessing routinely available information in the patients' medical records, and if necessary, by contacting the patient's GP.

4.5 End of Study Definition

The study will end after a total of 30 evaluable patients with complete data collection have been enrolled.

5. Laboratories

Not applicable

6. Assessment of Safety

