3.1 Sample size

In this single-centre study we wish to analyse 40 consecutive patients in whom a complete set of data can be obtained. From our previous experiences the incidence of AF in our intensive care unit is approximately 13.8%. Therefore in a sample size of 40 patients we would expect 2-3 patients to develop AF. This would allow us the opportunity to investigate any correlation between the changes in HRV preceding the onset of AF and investigate our secondary objectives to inform a larger clinical trial.

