4.3 Schedule of study procedure

With informed consent, the following routinely recorded clinical and laboratory data will be collected:

- Baseline demographics and comorbidities
- Administration of beta blockers or anti-arrhythmics
- Administration of sedative agents (general anaesthetics/opioids/benzodiazepines)
- Reasons for admission to ICU
- Daily biochemistry and haematology results
- Severity of illness scores, including APACHE II and daily SOFA scores
- Daily CAM ICU scores / delirium
- Daily cardiac rhythm as per nursing entry or clinical diagnosis
- Daily clinical parameters, including medications (vasopressors/ionotropes/steroids/muscle relaxants) and organ support
- Daily AKI stage, including treatment with RRT

After obtaining informed consent, continuous ECG data will be recorded using the two different devices. ECG data will then be processed to derive HRV using the methodology described by the European Society of Cardiology Taskforce guidelines.² Processing of ECG data entails checking

for and removal of extrasystole and ectopic beats with interpolation of QRS complexes as described elsewhere.² Continuous 24 hour ECG recording will then be divided into 5 minute epochs for which short term HRV values will be calculated. HRV will be calculated in the time domain, frequency domain and non-linear domains for each 5 minute epoch. Entire 24 hour ECG recordings will be used for long term HRV measures in the time domain, frequency domain and non-linear domains as described the Taskforce guidelines.² HRV data will then be analysed according to that described in the statistical methodology and analysis section. HRV data will be calculated by the Medical Engineering and Clinical Physics department at the Royal Liverpool and Broadgreen University Hospital. They will be blinded to any patient identifiable or clinical information.

Daily data will be collected until day 5 in ICU, day of discharge from ICU or day of death (depending on what occurs first). In addition, we will record ICU and hospital length of stay, ICU and hospital mortality and occurrence of arrhythmias during ICU stay, after 30 days, and after 90 days following enrollment. Data will be collected by accessing routinely available results in the patients' medical records, and if necessary, by contacting the patient's General Practitioner (GP).

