Appendix 2 – Information with regards to Safety Reporting in Non-CTIMP Research

	Who	When	How	To Whom
SAE	Chief Investigator	Report to sponsor within 24 hours of learning of the event Report to the MREC within 15 days of learning of the event	SAE report form for non-CTIMPs, available from NRES website.	Sponsor and MREC
Urgent Safety Measures	Chief Investigator	Contact the sponsor and MREC immediately Within 3 days	By phone Substantial amendment form giving notice in writing setting out the reasons for the urgent safety measures and the plan for future action.	Main REC and sponsor Main REC with a copy also sent to the sponsor. The MREC will acknowledge this within 30 days of receipt.
Progress Reports	Chief Investigator	Annually (starting 12 months after the date of favourable opinion)	Annual progress report form (non-CTIMPs) available from the NRES website	Main REC
Declaration of the conclusion or early termination of the study	Chief Investigator	Within 90 days (conclusion) Within 15 days (early termination) The end of study should be defined in the protocol	End of study declaration form available from the NRES website	Main REC with a copy to be sent to the sponsor
Summary of final Report	Chief Investigator	Within one year of conclusion of the research	No standard format However, the following Information should be included: Where the study has met	Main REC with a copy to be sent to the sponsor

			its objectives, the main findings and arrangements for publication or dissemination including feedback to participants	
--	--	--	--	--

12. References

2. Guidelines Heart rate variability Standards of measurement, physiological interpretation, and clinical use. *Eur. Heart J.* **17**, 354–381 (1996).
3. Karmali, S. N., Sciusco, A., May, S. M. & Ackland, G. L. Heart rate variability in critical care medicine: a systematic review. *Intensive Care Med. Exp.* **5**, 33 (2017).
4. McCraty, R. & Shaffer, F. Heart Rate Variability: New Perspectives on Physiological Mechanisms, Assessment of Self-regulatory Capacity, and Health Risk. *Glob. Adv. Heal. Med.* **4**, 46–61 (2015).

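### The protocol sets two sample sizes, 40 and 30, for patients with complete data; the AF count supporting the figure fits neither, and the end-of-study rule is unclear about day-90 follow-up

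*Protocol*

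**What the plan says.** **Number of patients.** The Number of Subjects row of the protocol synopsis gives 30 and does not say whether these are enrolled or evaluable. Section 3.1 (Sample size) says: "In this single-centre study we wish to analyse 40 consecutive patients in whom a complete set of data can be obtained". Section 4.5 (End of Study Definition) says: "The study will end after a total of 30 evaluable patients with complete data collection have been enrolled".

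**Support for the number.** Section 3.1 states that "the incidence of AF in our intensive care unit is approximately 13.8" per cent, and continues: "Therefore in a sample size of 40 patients we would expect 2-3 patients to develop AF". This is the only numerical argument for the sample size. The section adds that these cases would allow HRV changes before AF onset to be studied and would inform the secondary objectives.

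**Follow-up.** Section 4.4 says: "All patients will be followed up until day 90 after enrolment". Section 4.3 lists length of stay, mortality and "occurrence of arrhythmias during ICU stay, after 30 days, and after 90 days following enrollment" among the data to be recorded. Appendix 2 notes: "The end of study should be defined in the protocol".

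**The concern.** The sample size and the end of study are basic commitments of a protocol, and here they conflict. When the thirtieth evaluable patient is reached, section 4.5 says the study is finished and section 3.1 says it is 10 patients short. The team would have to choose between them during the study, with nothing in the protocol to guide the choice.

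The reason given for the number does not settle the matter either, because the stated AF count does not follow from the stated incidence at either size.

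The end-of-study rule raises a separate question. It is triggered by enrolment of the required patients, whereas follow-up runs for 90 days after enrolment. Appendix 2 counts the deadlines for the end-of-study declaration and the final report from the study's conclusion, so an unclear end makes those deadlines unclear too.

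**Working it through.** **Inputs (all from the protocol)**

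- N = 30: synopsis, and section 4.5 (evaluable, complete data).
- N = 40: section 3.1 (analysed, complete data).
- AF incidence p = 0.138, and 2-3 expected AF cases at N = 40: section 3.1.
- Follow-up of 90 days after enrolment for all patients: section 4.4.

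No alpha, power, effect size, SD, agreement margin or dropout rate accompanies the sample size. Neither 30 nor 40 can therefore be derived from a sample-size formula, and the AF expectation is the only figure that can be checked.

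**Step 1: the gap between the two targets.** (40 − 30) / 40 = 0.25. Stopping under section 4.5 leaves the study 25% below the number in section 3.1.

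**Step 2: could both be right, with 40 enrolled to yield 30 evaluable?** That would imply a 25% loss, since 30 / (1 − 0.25) = 40. Section 3.1, however, attaches 40 to patients analysed with complete data, and section 4.5 attaches 30 to evaluable patients with complete data. Both are counts after losses, and no loss rate is stated.

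**Step 3: the protocol's own AF figure.** Expected cases = N × p.

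| N | N × 0.138 | Stated | P(2 or 3 cases) | P(4 or more cases) |
|---|---|---|---|---|
| 40 | 5.52 | 2-3 | 0.16 | 0.82 |
| 30 | 4.14 | none given | 0.32 | 0.61 |

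The probabilities are exact binomial with p = 0.138. The stated 2-3 is not reproduced at 40, and it does not fit 30 either.

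**Step 4: what would give 2-3?** At 13.8%, N would have to be between 2 / 0.138 = 14.5 and 3 / 0.138 = 21.7. Alternatively, the incidence would have to be lower:

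- for N = 40: 2/40 = 5.0% to 3/40 = 7.5%;
- for N = 30: 2/30 = 6.7% to 3/30 = 10.0%.

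The protocol states no such rate.

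**Step 5: the end-of-study rule beside the follow-up.** There are two readings of section 4.5.

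- *Literal.* The study ends when the required patients have been enrolled. The last patient then has 0 of 90 follow-up days, and anyone enrolled in the preceding 90 days is incomplete. How many that would be depends on accrual, which the protocol does not give.
- *Qualified.* The 30 counted patients must first have complete data, possibly to day 90. Those patients are then covered. Enrolled patients who are not evaluable are still outside the rule, although section 4.4 follows all patients.

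Complete data is not defined, so the text does not decide between the two.

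**The case against.** **On the end of study.** A reader might infer that section 4.5 closes the study at enrolment and so loses the day-90 data of the last patients. The documents do not support that as a certainty. The rule counts only evaluable patients with complete data, and nobody has complete data on the day of enrolment. Since sections 4.3 and 4.4 make day 90 part of data collection, the rule can fairly be read as waiting for it. This objection stands, and the point is reduced to an unclear definition. Also, the 90-day items are not among the listed primary or secondary outcomes, although section 2.3 names mortality as a regression outcome.

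**On the consequence of 30 rather than 40.** A reader might infer that moving to 30 weakens the AF case made in section 3.1. Set against the protocol's own figure it does not: 4.1 expected cases at 30 exceeds the stated 2-3. A reader might also want a figure for lost precision in the limits of agreement. Section 3.1 makes no precision claim, and any such figure would have to assume one difference per patient, while the protocol describes repeated 5-minute epochs. No precision loss is claimed here.

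**On data-driven stopping.** Two targets could in principle let someone stop or continue after seeing results. The protocol describes no interim look and no success threshold, and this is an observational pilot. The realistic harm is an undefined accrual target.

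**On the AF rate.** The 13.8% is quoted for the unit, whereas the study requires sinus rhythm on admission and excludes known AF, so a lower rate may have been intended. That is possible, but the protocol neither says so nor gives the rate.

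None of these objections reconciles 40 with 30.

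**Conclusion.** The contradiction over N is certain. Sections 3.1 and 4.5 give different totals, 10 patients apart, for the same kind of patient, and no other part of the protocol resolves them. The synopsis agrees with 4.5 on the figure but not on what it counts, because its 30 is unqualified.

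The AF expectation is wrong on the protocol's own inputs: 5.5 at 40 or 4.1 at 30, against 2-3. This rests only on applying the stated 13.8% to the study's patients, as section 3.1 itself does.

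The end-of-study rule is badly fixed, not demonstrably harmful. It leaves open whether day-90 follow-up must be finished, and on either reading it does not clearly cover every enrolled patient.

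The conflict over N should be corrected before the protocol is used, because as written it cannot be followed. The timing of the end of study is a clarification to make in the same revision.

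**What to change.** 1. State one target N in the synopsis, section 3.1 and section 4.5, and say in each place whether it counts enrolled or evaluable patients. Thirty evaluable is the natural candidate, since 4.5 already says so. If 40 is intended, change the synopsis and 4.5. If N counts evaluable patients, enrolment may have to exceed it.
2. Restate the expected AF cases for that N: about 4.1 at 30 or about 5.5 at 40 with 13.8%. If 2-3 is what the investigators expect, state the lower incidence that gives it and where it comes from.
3. In section 4.5, define complete data and separate two events: recruitment stops when N evaluable patients have been reached, and the study ends when the last enrolled patient has completed day-90 follow-up.

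The cost is protocol wording only.

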6.1 Safety outcomes

We plan to collect only routinely available data. There will be no change in clinical practice. Patients will not receive any therapies or interventions that they would not have received if they had not been enrolled in the study and no tissue samples will be taken. Therefore we do not anticipate any adverse events or safety risks for patients, their personal consultees or members of the research team from participation in this study.

6.2 Safety of Heart rate variability monitoring devices

Device 1

Isansys Lifetouch Sensor is a fully CE marked medical device. The monitoring system includes single use wearable adhesive patches which are supplied in at least three sizes, depending on the age and size of the patient. Each Lifetouch provides the following clinical data continuously for a period of up to 5 days:

- Heart rate
- Respiration rate
- Real time heart rate variability
- Visualization of the ECG
- 3 axes accelerometer output

The Isansys Lifetouch Sensor is fully wireless and battery operated. The battery is not accessible to the patient or staff. All Isansys Lifetouch Sensor are single patient use and will be disposed off by following local procedures Information is transmitted wirelessly to a mobile patient status engine (ipad) via wifi and Low energy Bluetooth connectivity. The patient status engine Gateway is supplied in a protective medical grade bezel frame sealed in such a way to allow it to be cleaned with standard disinfecting/sterilising liquids or wipes. The device is safe with all other intensive care monitoring.

Device 2

Ambulatory Holter ECG monitoring is a standard of care used by the cardiorespiratory department. Ambulatory holter monitoring involves attaching a 12 lead ECG to the patient in the standard ECG lead configuration using standard ECG adhesive dots. Holter monitors record continuously for 72 hours onto a memory card and are entirely battery operated with no new electrical connection to the patient. Following 72 hours the memory card is analysed using software provided by the holter monitoring company. The software is of medical standard and provides HRV data, data on the number of interpretable episodes, data on ectopic beats and arrhythmias. Ambulatory holter monitoring is already in routine clinical use within the Royal Liverpool and Broadgreen University Hospital. They are CE marked and validate for use on patients.

6.3 Ethics Reporting

Approval from a Research & Ethics Committee (REC) will be sought. The REC will be informed about any changes according to the official National Research Ethics System regulations.

7. Steering Committee

	Name	Institution
1		
2		
3		
4		
5		
6		

8. Data safety and monitoring board

This is an observational study with no change in clinical practice. A Data safety and monitoring board will not be established.

9. Ethics & Regulatory Approvals

The study will be submitted centrally for consideration by a NRES approved Research Ethics Committee.

10. Data Handling

10.1 Confidentiality:

- All enrolled patients will have their hospital identification number and name recorded on a master list which will be held in a locked office in the Intensive Care Department. Only members of the study team will have access to the master list.
- All enrolled patients will be allocated a unique study number which will be used for referencing all of the data recorded.
- The Chief Investigator will act as ‘Custodian’ for all data collected.
- No patient identifiable details will be transferred outside the EU.
- No patient identifiable details will be included in the published study reports.
- All HRV analysis will be undertaken by the Medical Engineering and Clinical Physics department at the Royal Liverpool University Hospital. All data sent for analysis will be fully anonymised ECG data that will be coded with the unique study number. The Medical Engineering and Clinical Physic department will not have any patient identifiable information or access to patients clinical notes or information.
- Clinicians caring for the patient will have no access to the HRV data and all data analysis of Heart Rate Variability will be undertaken following discharge of the patient from the ICU

Information provided to General Practitioners:

- The patient’s general practitioner (GP) will only be informed about the patient’s enrolment at the request of the patient or their personal consultee (as described in the relevant patient, personal consultee and nominated consultee information sheets, as well as in the relevant consent and declaration forms).
- Patients, their personal consultees and nominated consultees may elect to opt-out of having the patient’s GP informed of their enrolment in the study.

10.2 Case Report Form

All data will be entered on a secure electronic database held at the University of Liverpool. The information technology (IT) infrastructure and will be supplied by the University of Liverpool and the Royal Liverpool University Hospital.

10.3 Record Retention and Archiving:

During the course of research, all records are the responsibility of the Chief Investigator. When the research trial is complete the records will be kept for a further 10 years (a requirement of the Research Governance Framework and Health Board Policy).

10.4 Compliance:

The study will be conducted in compliance with the principles of the Declaration of Helsinki (1996), and in accordance with all applicable regulatory requirements including but not limited to the Research Governance Framework, Trust and Research Office policies and procedures and any subsequent amendments.

10.5 Clinical Governance Issues

The study may be selected for audit by any method listed below:

- The project may be identified via the risk assessment process.
- An individual investigator or department may request an audit.
- A project may be identified via an allegation of research misconduct or fraud or a suspected breach of regulations.
- Projects may be selected at random. The Department of Health states that Trusts should be auditing a minimum of 10% of all research projects.
- Projects may be randomly selected for audit by an external organisation.
- Internal audits will be conducted by a sponsor's representative

10.6 Non-Compliance

Non-compliances may be captured from a variety of different sources including CRFs, communications and updates. The sponsor will maintain a log of the non-compliances to ascertain if there are any trends developing which to be escalated. The sponsor will assess the non-compliances and action a timeframe in which they need to be dealt with. Each action will be given a different timeframe dependant on the severity. If the actions are not dealt with accordingly, the R&D Office will agree an appropriate action, including an on-site audit.

11. Finance and Publication Policy

11.1 Finance

Funding will be sought from :

- NIHR
- Departmental resources
- The funder has no involvement in the protocol or design of the study.
- The results will remain intellectual property of the research team.

11.2 Publication policy

It is planned to publish the trial results, in mutual agreement with the investigator team, in a scientific journal and at international congresses. Publication of the results of the trial as a whole is intended. Requirements for authorship will follow AMA guidelines. Any publication will take account of the International Committee of Medical Journal Editors (ICMJE).

The study will also be registered in a public register in accordance with the recommendations of the ICMJE. Any published data will observe data protection legislation covering the trial subject and investigators. Success rates or individual findings at individual trial sites are known only to the responsible institution.

Publications or lectures on the findings of the present clinical trial either as a whole or at individual investigation sites must be approved by the PI in advance, and the responsible institution reserves the right to review and comment on such documentation before publication.

13. Appendices

Appendix 1: Analysis of HRV variables

Parameter	Units	Description	Normal range
SDNN	ms	Standard deviation of the NN intervals	101.19
SDANN	ms	Standard deviation of average NN intervals	41.47
pNN50	%	Percentage of successive RR intervals that differ by more than 50ms	18.80
RMSSD	ms	Root mean square of successive RR interval differences	0.08
LF power	ms ²	Absolute power of the low frequency band (0.04 – 0.15Hz)	2534.91
HF power	ms ²	Absolute power of the high frequency band (0.15 – 0.4Hz)	2592.32
VLF power	ms ²	Absolute power of the very low frequency band (0.033 – 0.04Hz)	8307.38
LF/HF ratio	%	Ration of LF to HF power	128.78
SD1	ms	Poincre plot standard deviation perpendicular to the line of identity	57.01
SD2	ms	Poincre plot standard deviation along the line of identity	134.13
SD1/SD2 ratio	%	Ratio of SD1 to SD2	2.49

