Chief Investigator	[name]. med. [name]
REC number	
Medical condition under investigation	Critical illness
Purpose of clinical trial	To investigate if two devices to monitor and capture Heart Rate Variability (HRV) and ECG data in Critically ill patients produce comparable results.
Primary objective	To describe the robustness of data on HRV obtained by two different monitoring systems during daily care of critically ill patients.
Secondary objective	
 1. To identify the most suitable and cost-efficient device for HRV monitoring in critically ill patients. 2. To define amendments in data capture and analysis required to proceed to a larger clinical trial
Number of Subjects	30 patients

Trial Design	Prospective observational feasibility study
Endpoints	
Primary outcome:
 
 • Number of interpretable HRV epoch episodes for each device and comparison between Isansys device and gold-standard holter monitoring (Isansys and Holter Monitor) 
Secondary outcomes:
 
 • Correlation of HRV time domain, frequency domain and non-linear HRV measures analysis between Isansys wireless monitoring patch and Holter monitoring • Correlation between HRV and onset of arrhythmias • Correlation between HRV and cardiorespiratory events (desaturation, drop in blood pressure >20%, change in ventilator settings) • Nurses' and medical staff's perception of the usability of both monitoring systems in daily routine practice
Main inclusion and Exclusion Criteria	
Inclusion criteria:
 
 • Adult patients ≥18 years • Expected stay in the ICU >48 hours • Sinus rhythm on ITU admission • Mechanically ventilated patients 
Exclusion criteria:
 
 • Non-ICU patient • History of Atrial Fibrillation • Inability to obtain consent
Randomization	Not applicable
Study procedure	
If all inclusion criteria are met and no exclusion criteria are present, patients will be eligible, invited to participate and informed consent will be sought.
 
Continuous ECG data will be recorded using two different devices. ECG data will then be processed to derive HRV using the methodology

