The European society of cardiology guidelines recognised a number of different HRV measures. Time domain measures are the simplest method of analysis of HRV. In a continuous ECG recording, the time between adjacent R wave peaks of QRS complexes is detected. This time interval is termed the N-N interval. Simple statistical tests are then applied to the N-N interval to determine the HRV, these include the standard deviation of the N-N interval (SDNN), square root of the mean squared differences of the N-N interval (RMSSD), the number of interval differences of successive N-N intervals greater than 50ms (NN50), and the proportion derived by dividing NN50 by the total number of NN intervals (pNN50).² Frequency domain measures

make use of power spectral density analysis and fast fourier transform analysis to provide information on how power distributes as a function of frequency.² This technique splits the ECG waveform into small subunits/epochs of time depending upon whether high frequency, low frequency or very low frequency measures are required (see below). The epochs of ECG waveform recording is then transformed from a temporal signal into a spectral representation whereby ECG signal is expressed as the sum of multiple sinusoidal waves of a given amplitude and frequency. These amplitudes are then plotted to give the power spectrum by plotting power versus frequency. Spectral components include frequencies measured HF domain(0.15-0.4Hz) thought to represent the parasympathetic input, LF domain (0.04-0.15Hz) thought to represent the sympathetic nervous system and the parasympathetic nervous system, VLF domain (<0.04Hz) and the ultra-low frequency (ULF) domains (<0.003Hz).²⁷ Measurement of the frequencies can be made in absolute values, but are often recorded as normalised units which represents the relative value of each power component in proportion to the total power minus the VLF component.⁸² Non-linear methods include measures such as the Poincare plot.² In the Poincare plot an individual's N-N interval is plotted against time and standard deviation used to interpret changes.⁹ The Poincare plot is described by two descriptors, SD1 is the fast beat-to-beat variability in the R-R intervals whilst SD2 describes the longer variability.^{9,2} SD1 reflects mainly the parasympathetic component of the autonomic nervous system, whilst SD2 reflects the parasympathetic and sympathetic components.⁹

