A recent systematic review of the use of HRV evaluated the methodology and design of HRV studies in critical care.³ Karmali et al revealed that over 230 studies have been published considering HRV in critical care.³ These studies published in the critical care literature differed vastly in trial design, methodology, confounding and data was inconsistently reported.³ Details on the time duration of recordings, epochs used in analysis and patient position was not reported in the majority of studies.³ Furthermore, many of the studies did not detail methods to detect artefact or describe how artefact was managed.³ These are significant failings, as ECG recording in the critically ill frequently suffers interference and physiological artefacts.³ Variability analysis should be free from artefact and suffer minimal noise:signal ratio.¹⁰ Artefact removal for HRV analysis often requires premature atrial beat or ventricular ectopic beat removal and appropriate interpolation of ECG QRS complexes. Alternatively techniques such as Poincare have been developed to allow automatic identification and removal of artefact.¹⁰

Each technique for the measurement of HRV represents a unique and distinct means of characterising a series of data in time.¹⁰ However, a number of factors can affect HRV measures regardless of the technique used. Standing and head up tilt are known to increase sympathetic activity. Similarly deep breathing and sighs have been shown to alter HRV indices as have alterations in blood pressure and the baroreflex.¹⁰ These factors should be taken into account

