3.2 Inclusion criteria

- Adult patients ≥ 18 years
- Expected ICU stay > 48 hours
- Sinus rhythm on admission
- Mechanically ventilated patients

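### Fixed HF and LF bands in ventilated patients: a breathing rate that crosses 9 or 24 breaths/min can shift HF, LF and LF/HF without autonomic change, and the plan keeps no breathing rate per epoch to show it

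*Protocol*

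**What the plan says.** **Bands.** Protocol Appendix 1 defines HF as "Absolute power of the high frequency band (0.15 – 0.4Hz" and LF as "Absolute power of the low frequency band (0.04 – 0.15Hz". The Introduction uses the same HF limits and gives them a meaning: "HF domain(0.15-0.4Hz) thought to represent the parasympathetic input". It reads LF as mixed sympathetic and parasympathetic input.

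**Population.** Section 3.2 lists "Mechanically ventilated patients" among the inclusion criteria.

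**Analysis.** The synopsis names as a secondary outcome "Correlation between HRV and cardiorespiratory events (desaturation, drop in blood pressure >20%, change in ventilator settings". Section 2.1 has a similar outcome, worded in terms of ventilatory support. The synopsis also makes a changed ventilatory setting an outcome of logistic regression with unnamed covariates. Section 2.3 lists other outcomes for that regression. The end of the Introduction makes the effect of mechanical ventilation on HRV one of the study's own questions.

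**Breathing.** The Introduction says "Similarly deep breathing and sighs have been shown to alter HRV indices" and asks that such factors be allowed for whichever technique is used. Neither section 2.3 nor section 4.3 returns to this.

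**Data capture.** Section 6.2 lists "Respiration rate" among the continuous outputs of the Isansys device. Section 2.3 describes only RR intervals being downloaded from it. Section 4.3 computes HRV per 5-minute epoch but collects clinical parameters and organ support daily, and names no breathing or ventilator rate.

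**The concern.** HF power tracks the respiratory component of heart rate only while breathing frequency lies inside the band. Ventilated patients can have their breathing rate altered by treatment, and ventilator changes are one of the events that HRV is to be related to. A single cause, a change of breathing rate, could therefore produce both the event and the shift in HF, LF or LF/HF.

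The study legitimately wants to describe what ventilation does to HRV. The risk lies in interpretation: a band-edge shift could be reported as a parasympathetic change, or as a predictor of ventilator events, in a pilot meant to inform a larger trial. As the protocol is written, the variable that would reveal this may not be exported. The department that computes HRV is also blinded to clinical information (sections 4.3 and 10.1), so it could not recover the rate from the notes.

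**Working it through.** **1. Band limits as breathing rates** (breaths/min = Hz × 60)
- HF: 0.15 × 60 = 9; 0.40 × 60 = 24.
- LF: 0.04 × 60 = 2.4; 0.15 × 60 = 9.

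**2. Expected size of a band-edge shift.** A sinusoidal respiratory oscillation of amplitude A has power A²/2. With background power B in the HF band, and ignoring interpolation loss, HF is A²/2 + B with breathing in band and B with breathing out of band. The fall is therefore by a factor of 1 + A²/(2B). The protocol gives neither A nor B, so both are assumptions.

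**3. First simulation** (5-minute series, A = 10 ms, a fixed 0.1 Hz component of 5 ms). Respiratory power is 10²/2 = 50 ms² and the slow component is 5²/2 = 12.5 ms².
- At 12–22/min: HF about 50, LF 13 ms².
- At 26/min: HF 0.5 ms², a fall of 50/0.5 = 100-fold; LF/HF goes from about 0.25 to about 25.
- At 8/min: HF 0.5 ms²; LF rises from 13 to 63 ms² (12.5 + 50 = 62.5); LF/HF is 63/0.5 = 126.

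**4. Second simulation, with more background** (heart rate 90/min, A = 15 ms, a 0.09 Hz component of 10 ms, beat noise SD 5 ms, 4 Hz resampling, Welch spectrum, 100 runs per rate; respiratory modulation held constant)

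| Breaths/min | HF (ms²) | LF (ms²) | LF/HF | SDNN (ms) | RMSSD (ms) |
|---|---|---|---|---|---|
| 8 | 6.6 | 159.6 | 24.2 | 13.7 | 9.6 |
| 10 | 110.3 | 52.6 | 0.48 | 13.7 | 10.4 |
| 16 | 97.4 | 53.1 | 0.54 | 13.7 | 13.5 |
| 23 | 79.0 | 52.6 | 0.67 | 13.7 | 17.0 |
| 24 | 56.2 | 51.9 | 0.92 | 13.7 | 17.5 |
| 25 | 6.6 | 52.5 | 8.0 | 13.7 | 17.9 |
| 30 | 6.4 | 52.8 | 8.2 | 13.7 | 19.8 |

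With no respiratory modulation at all, HF was also 6.6 ms². From 16 to 25/min HF falls 97.4/6.6 = 14.8-fold. Below 9/min LF roughly triples (159.6/53.1 = 3.0). Within the band the movement is moderate, from 110 to 79 ms² between 10 and 23/min, partly through interpolation. SDNN is flat throughout. RMSSD drifts with rate but has no break at 9 or 24.

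**5. Dependence on background.** If B equalled the respiratory power A²/2, the factor in step 2 would be 1 + 1 = 2. The break at the band edges is common to both simulations; its size follows from the assumed B.

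**6. Could the planned data show it?** The breathing rate exists as a device output (section 6.2), is not in the described download (section 2.3), and is not in the clinical list (section 4.3), which is daily where the HRV epochs last 5 minutes.

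**The case against.** **Nothing in the band definition is wrong.** The HF limits agree between the Introduction and Appendix 1, and the derivation follows a named guideline. Covariates and epoch rules are commonly left to a SAP, which may exist but is not shown. This stands for the modelling detail. It does not dispose of data capture: a SAP cannot use a rate that was never exported.

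**A reader might infer that HRV correlates with ventilator changes by construction.** The protocol does not support that. The artefact needs a breathing rate that crosses 9 or 24/min; no breathing or ventilator rates are given, and a ventilator change is not defined as a rate change. Time-domain, Poincaré and entropy measures are not defined by the band. Nor does the protocol say that the ventilator sets the breathing rate: no ventilation mode is stated, and section 4.2 provides for patients with capacity to consent.

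**The simulated sizes are not predictions.** This stands. The 100-fold figure reflects very low background power. The Gaussian-process preprocessing in section 2.3 was not modelled and could alter the size.

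**Excluding epochs or adjusting for rate can harm the analysis.** This also stands. Exclusion removes epochs selectively around the events under study, and where the event is a rate change, breathing rate is partly the outcome. Neither should be mandatory.

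**The Introduction speaks of deep breathing and sighs, not of rate.** True. It supports the general principle of allowing for breathing, and no more than that.

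**Conclusion.** The point holds in limited form. HF, LF, normalised units and LF/HF are open to confounding by breathing rate when it leaves 9–24/min, and the protocol relates these measures to ventilator changes without keeping the rate per epoch. The conversion to 9–24/min is exact. The fall in HF was about 15-fold in one simulation and about 100-fold in the other. Both assume constant respiratory modulation and a chosen background; more background gives a smaller fall.

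How often epochs lie out of band cannot be determined from the protocol. The primary outcome, a count of interpretable epochs, is little affected. So is the Bland-Altman comparison, because both devices record the same breathing. The matter concerns secondary analyses of a pilot. It is worth correcting because the remedy is cheap, and the needed data may be hard to recover if they are not exported.

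**What to change.** Amend sections 2.3 and 4.3 as follows.

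1. Export the respiration rate already recorded by the Isansys device together with the RR intervals, and link it to each 5-minute epoch.
2. Flag epochs with a rate outside 9–24/min and report their share. Count epochs without a usable rate separately, since the patch's robustness is itself under study.
3. Present the event analyses of HF, LF, normalised units and LF/HF, especially against ventilator changes, for all epochs and again for in-band epochs only.
4. State that a shift seen only when out-of-band epochs are included will not be read as autonomic.
5. Do not make respiration rate a mandatory covariate where the ventilator change is the outcome.

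Time-domain measures and the device comparison can keep all epochs. Clinical care does not change.

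**Cost:** one further export with time alignment, a line saying how the linkage fits with the blinding of the department that computes HRV, and fewer epochs in the restricted analysis. The change fits the study's stated objective of defining amendments to data capture and analysis.
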